#### Worst-Case Abnormality

The worst-case post-baseline categorized actual analysis value and the worst-case categorized change from baseline for QT and QTcF will be determined per subject, per parameter, and for each analysis period, using all non-missing post-baseline records (including unscheduled and FU visits).

The worst-case categorized actual analysis value is the category corresponding to the highest post-baseline actual value. In case of several equal highest post-baseline actual values, the earliest occurrence will be taken for the analyses and will be flagged in the listings.

The worst-case change from baseline is the category corresponding to the largest increase (positive change) from baseline. In case of several equal largest increase from baseline, the earliest occurrence will be taken for the analyses and will be flagged in the listings.

#### Treatment-Emergent Abnormalities

Actual value: An abnormal post-baseline abnormality is defined as treatment-emergent when the abnormality is worse compared to the abnormality at baseline or when there is a change in direction (from H to L or from L to H). When the baseline value is missing, post-baseline abnormalities are considered as treatment-emergent.

An abnormal category for change from baseline is always treatment-emergent.

### 6.3.3.4. Presentation of Results

No formal inferential statistics (p-values) will be derived.

Continuous parameters will be summarized by means of descriptive statistics (including 90% CI of the mean change) by parameter, treatment group and analysis window. Actual values and change from baseline will be tabulated separately.

Profile line plot by subject of all actual observed values using relative day (ADY) and profile plot on change from baseline by analysis window will be presented by treatment group. All values, including unscheduled visits will be presented in profile plot. If there is more than one visit on the same day, time will be considered to order them. Graphs of the mean (+- SE) actual values over time and of the mean (+- SE) change from baseline will be presented.

ECG will be further explored on the subset of subjects taking anti-malaria medications. Profile line plot by subject of actual observed values at baseline and at 1.5, 3 and 4.5 hours postdose will be presented by treatment group. In addition, profile line plot of the change from baseline to 1.5, 3 and 4.5 hours postdose will be presented.

The analysis of abnormalities will focus on assessments reported during the treatment period. Results reported during the screening period will only be listed.

Abnormalities of the actual values will be presented as shift tables of the worst-case abnormality versus the baseline abnormality. The table will be created per parameter, treatment group and analysis period.

A frequency table of the number (percent) of subjects with treatment-emergent worst-case abnormalities and the worst change per parameter, treatment group and analysis period will be presented.

A frequency table per treatment group and time point of the ECG interpretations as recorded in the case report form (CRF) will be provided.

A listing will be provided along with abnormality.

#### **6.3.4. Vital Signs**

##### **6.3.4.1. Available Data**

The following vital signs parameters will be analyzed: weight (kg), diastolic and systolic blood pressure (mmHG), heart rate (beats/min) and body temperature (C).

##### **6.3.4.2. Derivation Rules**

###### **Derived Parameters**

Not applicable.

##### **6.3.4.3. Abnormalities**

Vital signs data will be categorized according to the cutoffs provided in the SAP [Appendix II](#).

##### **6.3.4.4. Treatment-Emergent Principle**

A post-baseline abnormality class L or H is defined as treatment-emergent when it differs from the abnormality class at baseline. If the baseline result is missing, a post-baseline abnormality L or H will be considered as treatment-emergent.

An abnormal category for change from baseline is always treatment-emergent.

##### **6.3.4.5. Worst-Case Abnormality**

The worst-case post-baseline categorized actual analysis value will be determined per subject, per parameter and for each analysis period, using all non-missing post-baseline records (including unscheduled and FU visits).

The worst-case categorized actual analysis value is the category corresponding to the highest post-baseline actual value. In case of several equal highest post-baseline actual values, the earliest occurrence will be taken for the analyses and will be flagged in the listings.

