**Table 2 Analysis Periods**

Analysis Period	Start Analysis Period	End Analysis Period
Screening	Date of signing the ICF, with 00:00 added as time part	Date (time) of first IP administration - 1 minute
Treatment	Date (time) of first IP administration.	Study termination date (i.e. date of last contact), with 23:59 added as time part

The last analysis period will always end on the date of last contact.

For every subject, all assessments performed and all events occurring during the study are expected to have a (start) date (/time) between the date of informed consent (IC) signature and the last contact date. Obvious exemptions are historical records like medical history or concomitant therapies having started before the study.

Assessments and events will be allocated to one of these analysis periods by incidence, meaning placing the record (start) date and time between the matching start and end dates and times of the subject's own analysis periods, assuming completeness of all dates and times, or further determined by the presence of timing indicators such as tick boxes flagging AEs starting before/after first IP administration, or by worst-case considerations for AEs if needed. For the parameters for which the time of assessment was not planned to be collected, their assessment on the day of first IP administration will be considered as baseline and will be reported under the 'Screening' analysis period with the exception of AEs.

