#### **6.3.2.7. Worst-Case Principle**

##### **Toxicity Grading**

The worst-case post-baseline toxicity grade 0, 1, 2, 3 or 4 will be determined per subject, per laboratory test (and direction, increases and decreases) and for each analysis period, using all non-missing post-baseline records (including unscheduled and FU visits).

The worst-case toxicity grade is the highest toxicity grade corresponding to the highest laboratory test value (by direction, increases and decreases). In case of several equal highest post-baseline actual values, the earliest occurrence will be taken for the analyses and will be flagged in the listings.

- Grade 0: all post-baseline toxicity grades are classified as 0
- Grade 1: all post-baseline toxicity grades are classified as  $\leq 1$
- Grade 2: all post-baseline toxicity grades are classified as  $\leq 2$
- Grade 3: all post-baseline toxicity grades are classified as  $\leq 3$
- Grade 4: all post-baseline toxicity grades are classified as  $\leq 4$

If any record is missing, then the toxicity grade is considered as 'missing'.

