## Non-graded Abnormalities

The following worst-case post-baseline abnormalities L, N or H will be determined per subject, per laboratory test and for each analysis period, using all non-missing post-baseline records (including unscheduled and FU visits):

- L = low: at least one post-baseline result is classified as L.
- N = normal: all post-baseline results are classified as N.
- H = high: at least one post-baseline result is classified as H.

If, for a subject, both L and H are reported, the subject will be counted twice in the table: once with a worst-case L and once with a worst-case H.

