#### **6.3.4.6. Presentation of Results**

No formal inferential statistics (p-values) will be derived.

Continuous parameters will be summarized by means of descriptive statistics (including 90% CI of the mean change) by parameter, treatment group and analysis window. Actual values and change from baseline will be tabulated separately.

Graphs of the mean (+- SE) actual values over time and of the mean (+- SE) change from baseline will be presented.

The analysis of abnormalities will focus on assessments reported during the treatment period. Results reported during the screening or post-treatment (if defined) period will only be listed.

Abnormalities of the actual values will be presented as shift tables of the worst-case abnormality versus the baseline abnormality. The table will be created per parameter (and position if applicable), treatment group and analysis period.

A frequency table of the number (percent) of subjects with treatment-emergent worst-case abnormalities per parameter, treatment group and analysis period will be presented.

A listing will be provided along with abnormality.

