**Table 8 Gradings for Urine Analysis Parameters**

Parameter	L1	L2	L3	L4	H1	H2	H3	H4
Urine erythrocytes	NA	NA	NA	NA	≥ULN	≥10 cells/HPF	NA	NA
Urine protein	NA	NA	NA	NA	1+ proteinuria	2+ and 3+ proteinuria; urinary protein <3.5 g/24 hrs	urinary protein ≥3.5 g/24 hrs; 4+ proteinuria	NA
Urine glucose	NA	NA	NA	NA	>ULN (presence of glucose)	NA	NA	NA

LLN: lower limit of normal, ULN: upper limit of normal, NA: not applicable.

Any laboratory parameter with treatment-emergent (i.e., worsening from baseline) abnormalities of grade 2 or above (ie, H2/L2 or higher/lower) should be considered a 'marked laboratory abnormality'. Marked laboratory abnormalities should be described in a corresponding section of the CSR as per ICH E3 guidance, section 12.4.2.3.

**Appendix II: Vital Signs and Electrocardiogram grading****Table 9 Gradings for Vital Signs and Electrocardiogram Parameters**

Parameter	L1	L2	L3	L4	H1	H2	H3	H4
Systolic blood pressure (mmHg)	<90	<60	NA	NA	NA	≥140	≥160	≥180
Diastolic blood pressure (mmHg)	<60	<45	NA	NA	NA	≥90	≥100	≥120
Heart rate (bpm)	<60	<50	<40	NA	>100	>115	>130	NA
Body temperature (°C)	NA	<35	NA	NA	>38	NA	NA	NA
Respiratory rate (breaths per minute)	<12	NA	NA	NA	>20	NA	NA	NA
O 2 saturation (%)	<95	<90	NA	NA	NA	NA	NA	NA
Weight	≥7% decrease from baseline	NA	NA	NA	≥7% increase from baseline	NA	NA	NA
QTc interval on ECG (ms)	NA	NA	NA	NA	>450	>480	>500	NA
QTc change from baseline (ms)	NA	NA	NA	NA	NA	>30	>60	NA
PR interval on ECG (ms)	<110	NA	NA	NA	>200	NA	NA	NA
QRS complex on ECG (ms)	<60	NA	NA	NA	>120	NA	NA	NA

Source: FRM-MED-005/006, valid on 08JUL2020.

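### The vital-signs worst case is taken only from the highest post-baseline value, so low blood pressure, heart rate and temperature are under-reported in both worst-case tables

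*SAP*

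**What the plan says.** SAP 6.3.4.5 determines the vital-signs worst case per subject, parameter and analysis period from all non-missing post-baseline records, unscheduled and follow-up visits included. The selection rule is: "The worst-case categorized actual analysis value is the category corresponding to the highest post-baseline actual value". There is no lowest-value rule, and I found none for vital signs elsewhere in the SAP.

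The surrounding text works in both directions:

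- SAP Appendix II Table 9 has low grades. The heart-rate row reads "Heart rate (bpm) <60 <50 <40 NA >100 >115 >130 NA", that is L1 to L3 on the low side and H1 to H3 on the high side. Systolic pressure is graded low at <90 and <60, diastolic at <60 and <45, and temperature at <35. Weight is graded only by a change of at least 7% from baseline, in either direction.
- SAP 6.3.4.4: "A post-baseline abnormality class L or H is defined as treatment-emergent when it differs from the abnormality class at baseline".
- SAP 6.3.4.6: "Abnormalities of the actual values will be presented as shift tables of the worst-case abnormality versus the baseline abnormality". The treatment-emergent frequency table in the same section is also built from the worst case.
- SAP Table 2 ends the Treatment period at "Study termination date (i.e. date of last contact), with 23:59 added as time part", so the follow-up visit falls inside it.

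**The concern.** A maximum cannot represent a worst case when the harm may lie at the minimum. The SAP sets up low grades, then selects records in a way that hides them. A drop that reverses off drug disappears from both tables, and a subject who worsens in the low direction can be shown as improved.

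The sentence is identical to the ECG rule in SAP 6.3.3.3, which is limited in scope: "The worst-case post-baseline categorized actual analysis value and the worst-case categorized change from baseline for QT and QTcF will be determined per subject". Table 9 grades QTc only upwards, so taking the highest value is sound there. It is not sound for pressure, heart rate or temperature. SAP 6.6 gives no reason for a high-only rule.

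These are the only abnormality tables planned for vital signs. Safety is one of the few analyses kept after early termination (SAP 1).

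Two related gaps sit in the same subsections:

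- The ECG section also has a worst-case rule for change from baseline. The vital-signs section has none, although weight is graded only by change.
- In 6.3.4.4 the term for abnormality class could mean the Table 9 grade or only L versus H. On the second reading a rise from H2 to H4 is not treatment-emergent and drops out of that table, though not out of the shift table.

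**Working it through.** The plan gives no figure to reproduce. The check applies the printed rule and then sizes the loss under stated assumptions.

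**1. What the rule implies.** The category of the maximum is low only if the maximum is below the low cut-off, so every post-baseline value must be low. The grade shown is then that of the least low value.

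**2. Illustrative series, graded with Table 9.** The printed rule takes the category of the maximum; the by-direction rule takes the category of the minimum for the low side.

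| Series | Maximum → printed rule | Minimum → low side by direction |
|---|---|---|
| (a) Heart rate, baseline 55 (L1); 48, 47, 46, 45, then 64 at follow-up | 64 → normal | 45 (<50) → L2 |
| (b) Heart rate, baseline 72 (normal); 58, 39, 55, 57, 56 | 58 (<60) → L1 | 39 (<40) → L3 |
| (c) Systolic, post-baseline 118, 55, 121 | 121 → normal | 55 (<60) → L2 |

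In (a) one off-drug reading turns a shift from L1 to L2 into an apparent improvement from L1 to normal. In (b) the subject is counted as low, but at the mildest grade. In (c) the low value is lost.

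**3. Size.** A completer has five scheduled post-baseline records: Visits 2 to 5 and follow-up, from the schedule in SAP Table 1. A subject who stops early may have as few as two. The probability *p* of a low reading per visit and the within-subject correlation ρ are assumptions. The model is exchangeable latent normal:

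- q(u) = Φ[(Φ⁻¹(p) − √ρ·u)/√(1−ρ)], with u standard normal
- P(all *k* low) = E[q(u)^k]
- P(at least one low) = 1 − E[(1−q(u))^k]
- Share tabulated as low = P(all *k* low) / P(at least one low)

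With ρ = 0 this reduces to p^k / [1 − (1−p)^k]. For p = 0.05 and k = 2: 0.0025 / 0.0975 = 2.6%.

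| Records | p | ρ | At least one low | All low | Share tabulated |
|---|---|---|---|---|---|
| 5 | 0.05 | 0 | 22.6% | <0.0001% | 0.0% |
| 5 | 0.20 | 0.7 | 41.0% | 5.2% | 12.7% |
| 2 | 0.05 | 0 | 9.75% | 0.25% | 2.6% |
| 2 | 0.20 | 0.7 | 28.7% | 11.3% | 39.3% |

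**4. Sensitivity to stronger correlation.** With p = 0.20 and five records, the share is 20.3% at ρ = 0.8 and 34.1% at ρ = 0.9. With two records it is 60.0% at ρ = 0.9.

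**5. Comparison within the SAP.** SAP 6.3.2.7 derives laboratory toxicity worst cases separately for increases and decreases. For non-graded laboratory results it says: "If, for a subject, both L and H are reported, the subject will be counted twice in the table". Only the vital-signs section applies a one-sided rule to parameters graded on both sides.

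**The case against.** The strongest case on the other side concedes the text and argues that it matters little. These are two descriptive tables, without testing, in a stopped study planned for 30 subjects and reported in an abbreviated CSR. Low values remain in the listing with their abnormality flag and in the descriptive minima, and clinically significant ones are recorded as AEs. ECG heart rate has its own subject-level profile plots (SAP 6.3.3.4). All of that stands and limits the harm. It does not correct a wrong subject count, and vital signs have no subject-level plots of their own.

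The other objections:

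- **Size.** The range depends on where the correlation is capped, and it includes subjects already low at baseline, so it is not the treatment-emergent under-count. Both points are right. At ρ = 0.9 the loss is smaller but still substantial. The direction of the error does not depend on the assumptions.
- **Follow-up.** Pooling follow-up visits is the SAP's general convention and not a separate fault. Agreed: it is one way in which the direction gap operates. SAP 6.3.4.6 says post-treatment results, if such a period is defined, are only listed, but Table 2 defines none.
- **Weight.** Baseline is fixed, so the highest weight already gives the largest increase. Only weight loss is missed, which is the same defect again.
- **Abnormality class.** SAP 6.3.2.6 uses the same wording for non-graded laboratory results, so a class-based reading could be deliberate. This is a request for clarity, weaker than the main point.
- **Unseen material.** Provisions dropped after termination are marked in grey, which the extracted text does not show, and technical derivations sit in a separate document. Neither changes the rule as stated, and SAP 1 keeps the safety analyses.

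**Conclusion.** The concern holds. Followed exactly, SAP 6.3.4.5 gives wrong counts of low abnormalities in the shift table and the treatment-emergent table; this is an error in the rule, not a missing detail. That conclusion rests only on the SAP text and the Table 9 cut-offs.

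The size is illustrative and rests on the assumed per-visit probability and correlation. Even at a correlation of 0.9 about two thirds of subjects with a low reading are missed over five records (100 − 34.1 = 65.9%), and 40.0% over two (100 − 60.0), both at *p* = 0.20, the value most favourable to the rule in the assumed range. It should be fixed before the tables are produced, but it does not touch the primary efficacy analysis or AE reporting.

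**What to change.** - In SAP 6.3.4.5, derive the worst case separately by direction from all non-missing post-baseline records: the lowest value for L grades and the highest for H grades. Count a subject in both directions if both occur, as SAP 6.3.2.7 does for non-graded laboratory results.
- Do not carry over the clause in SAP 6.3.2.7 that sets the toxicity grade to missing if any record is missing.
- Add a worst-case rule for percent change in weight, covering the largest decrease and the largest increase.
- In SAP 6.3.4.4, state that a post-baseline abnormality is treatment-emergent when its Table 9 grade is worse than at baseline or its direction changes. This matches SAP 6.3.2.6 for toxicity grades and 6.3.3.3 for ECG.

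The cost is about three sentences and the reprogramming of two descriptive tables. No new data are needed.

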#### **6.3.4.6. Presentation of Results**

No formal inferential statistics (p-values) will be derived.

Continuous parameters will be summarized by means of descriptive statistics (including 90% CI of the mean change) by parameter, treatment group and analysis window. Actual values and change from baseline will be tabulated separately.

Graphs of the mean (+- SE) actual values over time and of the mean (+- SE) change from baseline will be presented.

The analysis of abnormalities will focus on assessments reported during the treatment period. Results reported during the screening or post-treatment (if defined) period will only be listed.

Abnormalities of the actual values will be presented as shift tables of the worst-case abnormality versus the baseline abnormality. The table will be created per parameter (and position if applicable), treatment group and analysis period.

A frequency table of the number (percent) of subjects with treatment-emergent worst-case abnormalities per parameter, treatment group and analysis period will be presented.

A listing will be provided along with abnormality.

#### **6.3.5. Physical Examinations**

Physical examination results will only be listed.

#### **6.3.6. SARS-CoV-2 Infection**

Results of the SARS-CoV-2 infection test will be listed for the subjects who have at least one positive test.

#### **6.3.7. Subgroup Analyses**

No subgroup analysis is planned for this clinical study as the study sample size is too small.

### **6.4. Pharmacokinetic Analysis**

#### **6.4.1. Available Data**

Blood samples for the PK assessment of GLPG3970 should be collected on the visits specified in the Schedule of Assessments in [Section 2.5](#).

[figure not shown]
#### **6.4.2. Presentation of Results**

Descriptive statistics will be provided for GLPG3970 plasma level at each assessment time point. Observed predose concentrations ( $C_{\text{tau}}$ ) for GLPG3970 will be reported in the CSR. Individual GLPG3970 plasma concentrations with descriptive statistics will be presented by time point/interval.

Predose samples not collected within 21 to 27 hours after the previous drug intake, or that were taken after the drug administration at the site will be excluded from descriptive statistics and flagged in the table with appropriate footnoting. In case there was a missed dose within 3 days prior to the sample, it will also be excluded from descriptive statistics and flagged in the table with appropriate footnoting. The same will be done with postdose samples taken outside of the defined time intervals. Actual blood sampling times from the last drug intake will be listed.

#### **6.5. [REDACTED]**

##### **6.5.1. Available Data**

##### **6.5.2. Presentation of Results**

## 6.6. Changes to the Planned Analyses, not Covered by Protocol Amendments

- Section 2.2.2: As per the protocol secondary endpoint is “Observed GLPG3970 plasma trough concentrations (Ctrough)”. Replaced Ctrough with Ctau.
- The prednisolone conversion table in [Appendix XII](#) will be used instead of the version in the CSP.

## APPENDIX

### Appendix I: Laboratory: Toxicity Grading

The following tables contain a list of safety tests with associated gradings. There may be tests in this table that are not measured in this particular study.

**Table 6      Gradings for Hematology Parameters**

Parameter	L1	L2	L3	L4	H1	H2	H3	H4
Hemoglobin	<LLN	<10 g/dL; <6.2 mmol/L	<8 g/dL; <4.9 mmol/L	NA	>ULN	Increase in >2 g/dL above ULN	Increase in >4 g/dL above ULN	NA
Hematocrit	<LLN	NA	NA	NA	>ULN	NA	NA	NA
Mean corpuscular volume (MCV), mean corpuscular hemoglobin (MCH), mean corpuscular hemoglobin concentration (MCHC)	<LLN	NA	NA	NA	>ULN	NA	NA	NA
Platelet count - (assuming no platelet cluster)	<LLN	<75 x 10  /L	<50 x 10  /L	<25 x 10  /L	>ULN	>600 x 10  /L	>1000 x 10  /L	NA
Leukocytes	<LLN	<3.0 x 10  /L	<2.0 x 10  /L	<1.0 x 10  /L	>ULN	>20.0 x 10  /L	>100.0 x 10  /L	NA
% Polymorphonuclear Leukocytes + Band Cells	NA	NA	NA	NA	>ULN	≥90%	>95%	NA

Parameter	L1	L2	L3	L4	H1	H2	H3	H4
Neutrophils	<LLN	<1.5 x 10  /L	<1.0 x 10  /L	<0.5 x 10  /L	NA	NA	NA	NA
Eosinophils	NA	NA	NA	NA	>ULN	>5.0 x 10  or eosinophils >5%	NA	NA
Lymphocytes	<LLN	<0.8 x 10  /L	<0.5 x 10  /L	<0.2 x 10  /L	>ULN	>4.0 x 10  /L	>20.0 x 10  /L	NA
Red blood cells	<LLN	NA	NA	NA	>ULN	NA	NA	NA

**Table 7 Gradings for Blood Chemistry Parameters**

Parameter	L1	L2	L3	L4	H1	H2	H3	H4
Alanine aminotransferase (ALT)	NA	NA	NA	NA	>ULN	>3.0 x ULN	>5.0 x ULN	>8.0 x ULN
Aspartate aminotransferase (AST)	NA	NA	NA	NA	>ULN	>3.0 x ULN	>5.0 x ULN	>8.0 x ULN
Gamma-glutamyl transferase (GGT)	NA	NA	NA	NA	>ULN	>2.5 x ULN	>5.0 x ULN	>20.0 x ULN
Alkaline Phosphatase (total)	NA	NA	NA	NA	>ULN	>2.5 x ULN	>5.0 x ULN	>20.0 x ULN
Lactate dehydrogenase (LDH)	NA	NA	NA	NA	>ULN	NA	NA	NA
Total bilirubin	NA	NA	NA	NA	>ULN	>1.5 x ULN	>3.0 x ULN	>10.0 x ULN
Amylase	NA	NA	NA	NA	>ULN	>1.5 x ULN	>2.0 x ULN	>5.0 x ULN
Lipase	NA	NA	NA	NA	>ULN	>1.5 x ULN	>2.0 x ULN	>5.0 x ULN
Total protein	<LLN	<5.5 g/dL	<5.0 g/dL	NA	NA	NA	NA	NA
C-reactive protein (CRP)	NA	NA	NA	NA	>5mg/L	>10mg/L	>20mg/L	>30mg/L
Activated partial thromboplastin time (APTT)	NA	NA	NA	NA	>ULN	>1.5 x ULN	>2.5 x ULN	NA
Prothrombin time (PT)	NA	NA	NA	NA	≥1.10 x ULN	≥1.25 x ULN	≥1.50 x ULN	≥3.00 x ULN

Parameter	L1	L2	L3	L4	H1	H2	H3	H4
International normalized ratio (INR)	NA	NA	NA	NA	>1.2 x Baseline	>1.5 x Baseline	>2.5 x Baseline	NA
Creatinine	NA	NA	NA	NA	>ULN	>1.5 x ULN	>3.0 x ULN	>6.0 x ULN
Glucose ( fasting )	<LLN	<55 mg/dL; <3.0 mmol/L	<40 mg/dL; <2.2 mmol/L	<30 mg/dL; <1.7 mmol/L	>ULN	>125 mg/dL; ≥6.95 mmol/L	>250 mg/dL; ≥13.89 mmol/L	≥500 mg/dL; ≥27.75 mmol/L
Glucose ( non-fasting )	<LLN	<55 mg/dL; <3.0 mmol/L	<40 mg/dL; <2.2 mmol/L	<30 mg/dL; <1.7 mmol/L	>ULN	>160 mg/dL; ≥8.89 mmol/L	>250 mg/dL; ≥13.89 mmol/L	≥500 mg/dL; ≥27.75 mmol/L
HbA1c	NA	NA	NA	NA	> 6.0 %	> 6.5 %	NA	NA
Fasting insulin	<2.6 µU/mL or 18.1 pmol/L	NA	NA	NA	>24.9 µU/m or 172.9 pmol/L	NA	NA	NA
Cholesterol	NA	NA	NA	NA	>ULN	>300 mg/dL; ≥7.75 mmol/L	>400 mg/dL; ≥10.34 mmol/L	>500 mg/dL; ≥12.92 mmol/L
Low-density lipoprotein (LDL)	NA	NA	NA	NA	>ULN	≥160 mg/dL; ≥4.12 mmol/L	≥190 mg/dL; ≥4.90 mmol/L	NA
High-density lipoprotein (HDL)	<LLN	<40 mg/dL; <1 mmol/L	NA	NA	NA	NA	NA	NA

Parameter	L1	L2	L3	L4	H1	H2	H3	H4
Triglycerides	NA	NA	NA	NA	>ULN	>300 mg/dL; >3.42 mmol/L	>500 mg/dL; >5.7 mmol/L	>1,000 mg/dL; >11.4 mmol/L
Calcium (corrected for albumin)	<LLN	<8.0 mg/dL; <2.0 mmol/L	<7.0 mg/dL; <1.75 mmol/L	<6.0 mg/dL; <1.5 mmol/L	>ULN	>11.5 mg/dL; ; >2.9 mmol/L	>12.5 mg/dL; ; >3.1 mmol/L	>13.5 mg/dL; ; >3.4 mmol/L
Ionized calcium	<LLN	<1.0 mmol/L	<0.9 mmol/L	<0.8 mmol/L	>ULN	>1.5 mmol/L	>1.6 mmol/L	>1.8 mmol/L
Sodium	<LLN	<130 mEq/L; <130 mmol/L	<125 mEq/L; <125 mmol/L	<120 mEq/L; <120 mmol/L	>ULN	>150 mEq/L; >150 mmol/L	>155 mEq/L; >155 mmol/L	>160 mEq/L; >160 mmol/L
Chloride	<LLN	NA	NA	NA	>ULN	NA	NA	NA
Potassium	<LLN	NA	<3.0 mmol/L	<2.5 mmol/L	>ULN	>5.5 mmol/L	>6.0 mmol/L	>7.0 mmol/L
Phosphate	<LLN	<2.0 mg/dL; <0.65 mmol/L	<1.4 mg/dL; <0.45 mmol/L	<1.0 mg/dL; <0.32 mmol/L	>ULN	NA	NA	NA
Creatine phosphokinase (CPK)	NA	NA	NA	NA	> ULN	>2.5 x ULN	>5 x ULN	>10 x ULN
Uric acid	NA	NA	NA	NA	>ULN	≥10 mg/dL; ≥0.59 mmol/L	≥12 mg/dL; ≥0.71 mmol/L	≥15 mg/dL; ≥0.89 mmol/L
Albumin	<LLN	<30 g/L	<20 g/L	NA	NA	NA	NA	NA
eGFR (or Cr/Cl)	<LLN	<60 ml/min/ 1.73 m 	<30 ml/min/ 1.73 m 	<15 ml/min/ 1.73 m 	NA	NA	NA	NA

Parameter	L1	L2	L3	L4	H1	H2	H3	H4
Blood urea nitrogen (BUN)	NA	NA	NA	NA	>ULN	>2.5 ULN	>5 ULN	>10 ULN

Parameter	L1	L2	L3	L4	H1	H2	H3	H4

